### **1. Study Instruments:**

**Assessment of Intake of Target Foods:** Targeted healthy foods included FV (fresh, canned, frozen). Parents were instructed to omit energy-dense toppings/sauces on FV. Targeted less healthy foods included 1) SSS (e.g., all types of chips, popcorn, pretzels, party mixes, ice cream, candy, cookies, cakes/pies, sweet rolls, pastries) and 2) SSB (e.g., sugar-sweetened sodas, fruit drinks/punches and fruit juices, sport drinks, and energy drinks). Dietary goals were set by parents and tailored to children's preferences and sensory sensitivities. Children's intake was assessed at baseline and at the end of the intervention using the telephone-based 24-hr dietary recall method; the gold standard for self-reported intake. Each assessment consisted of 3 unannounced recalls (2 weekdays, 1 weekend day), which was conducted by research dietitians from the CHOP Center for Human Phenomic Science. Dietitians were blinded to families' group assignment. During each recall, they asked parents, with help from the children, to describe all foods/beverages consumed by their children during the prior 24 hours and provide detailed information about portion sizes/preparation methods. Data were analyzed for daily FV intake (servings/day; cup equivalents) and calories consumed from SSB/SSS using the University of Minnesota Nutrition Coordinating Center's Food and Nutrient Database. All data were averaged across the 3 days.

**Child Height and Weight Measures:** At baseline and at the end of the intervention, children had their heights and weights measured. Measurements were taken in triplicate with a portable scale/stadiometer by a trained staff member in children's homes with children wearing light clothing (no shoes). Child age- and sex-specific BMI percentiles and z-scores were calculated using the CDC Growth Charts 2000. Children were classified as normal-weight (BMI-for-age 5–84th percentile), overweight (BMI-for-age 85–94th percentile), or obese (BMI-for-age ≥95th percentile).

**Questionnaires:** During the telephone screening, parents were asked to complete the Picky Eating subscale of the Child Feeding Questionnaire (CFQ), which consists of the following items: 1) "My child's diet consists of only a few foods"; 2) "My child is unwilling to eat many of these foods that our family eats at mealtimes"; 3) "My child is fussy / picky about what she eats." A child was defined as a picky eater if the parent endorsed at least 2 out of the 3 items. Parents were asked follow-up questions to determine whether a child's pickiness was related to the intervention's targeted healthy and less healthy foods. During the baseline visit, parents completed a Demographic Questionnaire and the 38-item Sensory Profile, 2nd Edition (short form), which assessed children's sensory processing abilities, including oral sensory sensitivity (e.g., sensitivities to food tastes/textures). Children were categorized as having typical or atypical oral sensory sensitivity based on classifications specified by Dunn.

**Evaluation of mHealth Intervention:** We evaluated the mHealth intervention using the following strategies: 1) Engagement: The mHealth platform kept an automatic log of all user activities, including subjects' log-in frequency, duration of use, features used, goal/progress tracking, number of points and rewards awarded, etc. These log files were automatically generated by the software and enabled us to monitor participants' compliance with the intervention; 2) Semi-structured interviews and brief questionnaires: At the end of the intervention, parents in the intervention group were asked to complete a semi-structured interview and a brief questionnaire, which asked them to provide feedback on the usefulness and relevance of the mHealth technology, parent and child engagement and motivation, and to evaluate key features of the mHealth intervention such as user friendliness, ease of use, and technical or time barriers. Children in the intervention group were asked to complete a brief questionnaire that assessed level of enjoyment, learning, and understanding of the mHealth technology

#### **2. Group Modifications:**

Parents in the education group were not asked to participate in the evaluation of the mHealth intervention.

#### **3. Method for Assigning Subjects to Groups:**

Statisticians of the Biostatistics Consulting Unit at the Penn School of Nursing carried out the randomization of participants into the intervention and education groups. They used a randomized block design to produce groups that are comparable in weight status.

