## **CHARACTERISTICS OF THE STUDY POPULATION:**

### **1. Target Population and Accrual:**

The study aimed to include 46 racially/ethnically diverse boys/girls with ASD, ages 6-10 years, and their parent/legal guardian (referred to 'parent' for ease of use). The age range was chosen to ensure that children have the cognitive skills to interact with the technology. Our multi-pronged recruitment plan utilized the CHOP health system and community-based organizations throughout Philadelphia. The study was open to subjects of all races and ethnicities. Parents must be the children's primary caregiver (i.e., person responsible for grocery shopping/feeding). Children and parents must have access to a smartphone or tablet to be eligible for study participation. For this exploratory trial, we aimed to recruit a well-defined, homogenous group of children to determine the efficacy of this intervention. Only children without significant developmental delay (i.e., IQ  $\geq 80$  and comparable verbal ability) were enrolled to increase the likelihood of comprehension and engagement with the technology. Children with a range in weight were included to explore if the intervention is equally effective in normal-weight and overweight/obese children.

This project's primary purpose was to evaluate feasibility, acceptability, and utilization of the mHealth intervention and to obtain preliminary effect size estimates. A power analysis was conducted (PASS software, Version 11, NCSS LLC, Kaysville, UT) for Primary Aim 2 using 3-month changes in intake of targeted healthy foods (FV) as the primary outcome variable. The estimated mean ( $\pm SD$ ) for baseline FV intake ( $2.57 \pm 1.20$  servings/day) was derived from our pilot study in children with ASD. Based on this estimate, a sample size of 46 children and an attrition rate of 10%, we had 80% power to detect a statistically significant increase in FV intake of 1.1 servings/day (or 43%) in the intervention group relative to the education group at the alpha 0.05 level, based on a two sample t-test. The magnitude of this increase is comparable to that achieved in behavioral interventions in TDC and represents ~one-fifth of the RDA of FV for children of that age.

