### **5. Statistical Analysis:**

To test Primary Aim 2, a mixed-effects linear model with repeated measures assessed 3-month changes in children's FV (cups/day) and SSB/SSS (calories/day) intake by group. The fixed factor effects in all models were group (incentive, control) and time (baseline, month 3). The group-by-time interaction was tested and removed if not significant. Analysis of covariance assessed if the intervention is equally successful in boys/girls, children of various ages/weights, and children with typical/atypical sensory sensitivity. For Secondary Aim 2, data from log files and questionnaires were analyzed and open-ended responses from the semi-structured interview were coded, compiled into categories, and grouped into themes using a general inductive approach.  $P$  values were two-sided and  $P<0.05$  was considered significant for all tests. First, analyses were conducted with all participants included. Then, a sensitivity analysis were conducted that included only participants who actively participated in the intervention.

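### Randomisation was blocked on weight status but the primary intake models leave it out; if weight status predicts change in intake, the reported standard error is too wide.

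*Combined protocol and SAP*

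**What the plan says.** Method for Assigning Subjects to Groups describes the allocation: "They used a randomized block design to produce groups that are comparable in weight status". Block size, allocation ratio and the weight levels used are not given.

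Statistical Analysis describes the primary model as "a mixed-effects linear model with repeated measures assessed 3-month changes in children's FV (cups/day) and SSB/SSS (calories/day) intake by group". It continues: "The fixed factor effects in all models were group (incentive, control) and time (baseline, month 3"), and then: "The group-by-time interaction was tested and removed if not significant". Weight enters the analysis in one other place: "Analysis of covariance assessed if the intervention is equally successful in boys/girls, children of various ages/weights", along with sensory sensitivity.

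Target Population and Accrual says a range of weights was enrolled "to explore if the intervention is equally effective in normal-weight and overweight/obese children", and gives as part of the trial's primary purpose "to obtain preliminary effect size estimates". Study Instruments defines three weight categories (normal-weight, overweight, obese). No section adds weight status to the primary models or gives a reason for leaving it out.

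**The concern.** Blocking on a factor removes its chance imbalance between arms, so the true variability of the estimated effect falls if the factor predicts the outcome analysed. A model without the factor leaves that variation in the residual and reports a standard error as if the imbalance could still occur. The test then rejects less than 5% of the time under the null, and the confidence interval is wider than the design warrants.

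The subgroup analysis does not repair this, because it asks whether the effect differs by weight and leaves the primary estimate unadjusted.

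Two features of the plan make this worth raising. Effect size estimates are a stated product of the trial, and 46 children leave little precision to spare. Also, the group-by-time term carries the treatment effect and is dropped when not significant, so a conservative test makes its removal more likely.

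**Working it through.** **Inputs from the documents.** 46 children, 10% attrition, difference of 1.1 servings/day, SD 1.20 (given for baseline intake), alpha 0.05, two-sample t-test (all Target Population and Accrual); two-sided tests (Statistical Analysis).

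**Assumptions.** 1:1 allocation; the block design read as permuted blocks within weight strata; SD 1.20 applied to change in intake. R², the share of variance in change explained by weight status, is not given and is varied.

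**The plan's own figure.** 46 × 0.9 = 41.4, so about 41 analysed. SE = 1.20 × √(1/20 + 1/21) = 0.375. The noncentral t-test gives 80.6% power with 20 + 20 and 81.6% with 20 + 21, in line with the stated 80%.

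**Effect of adjusting, by formula.** Adjusted SE = 0.375 × √(1 − R²). The unadjusted SE is larger by the factor 1/√(1 − R²).

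**Simulation.** 20,000 trials per setting: 46 randomised in blocks of 4 within weight stratum, random loss to 41, least squares on change with and without stratum terms. Ranges cover two strata (50/50) and three (50/25/25).

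| R² | Adjusted SE (formula) | Unadjusted SE larger by | Power unadjusted | Power adjusted | Type I error unadjusted |
|---|---|---|---|---|---|
| 0% | 0.375 | 0% | 81.0–81.5% | 80.7–81.1% | 5.1–5.2% |
| 5% | 0.365 | 2.6% | 81.8–82.3% | 82.8–83.4% | not run |
| 10% | 0.356 | 5.4% | 82.2–82.4% | 84.6–85.0% | 3.8–4.2% |
| 20% | 0.335 | 11.8% | 83.2–83.9% | 89.0–89.1% | 3.1–3.5% |

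Adjusted type I error stays at 4.7–5.3%. Monte Carlo error is about 0.3 points for power and 0.15 for type I error. Unadjusted power rises with R² because blocking still steadies the estimate; only the reported SE fails to show it. At R² = 20% the unadjusted model reports 0.374–0.375 against an actual SD of 0.343, while the adjusted model reports 0.335 against 0.337–0.338.

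**Confidence interval.** Half-width unadjusted: 2.02 × 0.375 = 0.76 servings/day. Adjusted with two extra degrees of freedom spent: 2.03 × 0.356 = 0.72 at R² = 10%, and 2.03 × 0.335 = 0.68 at 20%.

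**Is blocking the cause?** A second simulation (three strata, 60/20/20) at R² = 20% compared allocation methods. Under simple randomisation the unadjusted SE is right: 0.374 against 0.374, type I error 5.0%. Under blocking it is 0.375 against 0.339, type I error 3.4%. So the excess comes from blocking and then omitting the factor.

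**Which term is needed?** With two time points and complete data, group-by-time is the between-arm difference in mean change, and a weight main effect cancels when each child's two values are subtracted. Mixed-model fits (60 data sets of 42 children, two weight levels) gave these mean group-by-time SEs:

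| Weight status shifts | No weight term | Main effect only | Weight-by-time |
|---|---|---|---|
| Level only | 0.364 | 0.364 | 0.364 |
| Change (about 10% of variance) | 0.392 | 0.392 | 0.373 |

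**The case against.** The strongest reply is that little is at stake. Nothing is biased, and unadjusted power stays at 81–84% throughout, so the loss is precision beyond what was planned. The sizeable gain needs R² near 20%, which nothing in the documents supports; at 5% it is about 1 point. The trial calls itself exploratory. All of this stands, and it limits the point to a recommended improvement. It does not remove it, because the cost if weight status is irrelevant is a fraction of a point.

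Four further points:

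- **Timing.** The document is in the past tense. If the primary results already exist, the primary model should not be replaced on this ground. This stands and is reflected in the fix.
- **Alternative model.** A month-3 model with baseline intake as covariate brings a separate gain. In one check (within-stratum correlation 0.5, weight status shifting level only, 10% of variance), the SE went from 0.349 for change to 0.311 with the baseline covariate, then only to 0.306 with weight status added. It should not be credited to the blocking factor.
- **Level-only effects.** The statement that these do no harm applies to group-by-time. Once that term is removed, the SE of the remaining group effect does depend on level. True, but that effect is not the treatment effect on change, and the removal rule is a separate problem.
- **Weight levels.** Two weight groups in one section and three in another need not conflict, since the two may collapse the three. Agreed; the gap is that the blocking levels are unstated.

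**Conclusion.** The concern holds. The factor used to block the allocation is absent from the primary models. The consequence is conditional: the interval could be wider than the design warrants, by about 5% at R² = 10% and 12% at 20%, and not at all at 0%. Matching power gains from adjusting are 2–3 points and 5–6 points, against a loss of 0.3–0.4 points if weight status is irrelevant. This is a matter of precision and of matching analysis to design; validity is not in question.

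The figures rest on the assumed R², an SD of 1.20 for change, 1:1 allocation and blocking within weight strata. Blocks of 8 or 12 in place of 4 made no material difference. The omission itself is clear from the text; its size in this trial is unknown.

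**What to change.** In the primary FV and SSB/SSS models, add weight status and weight-status-by-time as prespecified terms, kept regardless of significance. An alternative is weight status as a factor in a month-3 model with baseline intake as covariate, but that changes the primary model and should be chosen on its own merits.

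Use the weight-status levels used at randomisation and state them: Target Population and Accrual contrasts normal-weight with overweight/obese children, while Study Instruments has three categories.

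If the primary analysis has already been run, report the weight-adjusted model beside it as a labelled sensitivity analysis.

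Cost: one line of SAP wording for the mixed-model option and one or two degrees of freedom. No new data are needed, since height and weight were measured at baseline.

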#### **4. Administration of Surveys and/or Process:**

Telephone Screening: The telephone screening involved review of information to determine initial eligibility criteria. In addition, during the screening phone call verbal consent was obtained for completion of the baseline dietary recall interviews with the parent prior to the baseline visit.

Baseline Study Visit: The baseline study visits included the full written consenting/assenting process, measurement of child height and weight, completion of questionnaires, and, for families in the intervention group, orientation to the technology and installation of the software on participants' smartphones. This visit lasted approximately 90 minutes.

3-Month Study Visit: The 3-month study visit (end of intervention) included measurement of child height and weight and, for families in the intervention group, a semi-structured interview and two brief questionnaires to evaluate the mHealth intervention. This visit lasted approximately 60 minutes.

Dietary Recalls: Children's intake was assessed at baseline and at the end of the intervention using the telephone-based 24-hr dietary recall method. Each assessment consisted of 3 unannounced recalls (2 weekdays, 1 weekend day), which were conducted by research dietitians from the CHOP Center for Human Phenomic Science. Each recall lasted approximately 20 minutes.

### **STUDY PROCEDURES:**

#### Randomized Controlled Trial:

Intervention Group: At baseline, parents in the intervention group received a comprehensive parent training which 1) provided skills training in the five core behavior change strategies and 2) explained the nutritional goals and targeted foods/beverages for the study. The training modules were designed by a behavioral strategist and clinical psychologist, a clinical psychologist, and a nutrition scientist. The modules reviewed examples of the targeted foods/beverages and provided training in how to present feeding opportunities, incorporate healthy target foods in daily family meals and snacks, and substitute the less healthy target foods/beverages for healthier options. The training also addressed how parents can overcome resistance in children trying new foods using differential attention and positive reinforcement techniques. It included instructions on how to use the mHealth technology and showed parents how to set dietary goals, select real-life prizes, award points, and determine the allotted timeframe and number of points it will take for the child to earn a prize. The mHealth intervention was personalized for each child to take into account individual differences in children's food preferences, level of picky eating, sensory sensitivities, etc. Specifically, the mHealth technology enabled parents to tailor the selection of food choices available to the child and customize, with input from the child, food preparation methods (e.g., raw or cooked, seasonings to be added). The training also included a training module for the children to show them how to navigate the technology, orient them to the nutrition intervention, and explained the reward system. Research staff assisted with the software installation on the families' electronic devices and parents were encouraged to use the technology as frequently as possible during meal and snacks times over the course of the 3-month intervention.

**Education Group:** Parents in the education group were instructed to review a handout, which provided general educational information about healthy eating. It explained the nutritional goals and targeted foods/beverages for the study, but it did not provide parent skills training in the core behavioral strategies. This condition mimiced what families may receive during a routine well-child visit.

Parents in both groups were encouraged to promote children's intake of the healthy target foods and limit their intake of the less healthy target foods/beverages on a daily basis for the next 3 months.

### **5. Statistical Analysis:**

To test Primary Aim 2, a mixed-effects linear model with repeated measures assessed 3-month changes in children's FV (cups/day) and SSB/SSS (calories/day) intake by group. The fixed factor effects in all models were group (incentive, control) and time (baseline, month 3). The group-by-time interaction was tested and removed if not significant. Analysis of covariance assessed if the intervention is equally successful in boys/girls, children of various ages/weights, and children with typical/atypical sensory sensitivity. For Secondary Aim 2, data from log files and questionnaires were analyzed and open-ended responses from the semi-structured interview were coded, compiled into categories, and grouped into themes using a general inductive approach.  $P$  values were two-sided and  $P<0.05$  was considered significant for all tests. First, analyses were conducted with all participants included. Then, a sensitivity analysis were conducted that included only participants who actively participated in the intervention.

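### The two-visit group-by-time test of FV and SSB/SSS intake does not adjust for baseline; adjusting, and always reporting the estimate, is a nearly free gain in precision

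*Combined protocol and SAP*

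**What the plan says.** The Statistical Analysis section states that "a mixed-effects linear model with repeated measures assessed 3-month changes in children's FV (cups/day) and SSB/SSS (calories/day) intake by group". On the model terms it says: "The fixed factor effects in all models were group (incentive, control) and time (baseline, month 3"). It then adds: "The group-by-time interaction was tested and removed if not significant". Covariance adjustment is named only for the effect-modifier questions: "Analysis of covariance assessed if the intervention is equally successful in boys/girls", and likewise for age, weight and sensory sensitivity.

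The Study Instruments section confirms that baseline values exist: "intake was assessed at baseline and at the end of the intervention using the telephone-based 24-hr dietary recall method", with three recalls averaged at each assessment.

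The Target Population and Accrual section describes the project's "primary purpose was to evaluate feasibility, acceptability, and utilization of the mHealth intervention and to obtain preliminary effect size estimates". The power analysis there is for FV, "using 3-month changes in intake of targeted healthy foods (FV) as the primary outcome variable". It takes 46 children, 10% attrition, a two-sample t-test at 0.05 and a pilot baseline intake of 2.57 (SD 1.20) servings/day, and concludes that "we had 80% power to detect a statistically significant increase in FV intake of 1.1 servings/day (or 43"%). It gives no correlation between visits, no SD of change and no month-3 SD.

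**The concern.** In the planned model, baseline intake is one of the two outcome values. With a free group effect, two visits and complete data, the group-by-time term equals the between-group difference in mean change. Baseline is therefore subtracted in full, not adjusted for. Subtracting it in full adds noise unless the regression of month-3 on baseline intake has a slope near 1, which is unlikely for a few dietary recalls per visit.

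At stake is the precision of the effect estimate. Preliminary effect sizes are part of the stated purpose, and only about 41 completers are expected. The rule for removing the interaction makes this worse. When the term is not significant, the fitted model no longer contains a direct estimate of the month-3 effect, and what remains mixes in the baseline visit, where randomisation makes the expected difference zero.

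**Working it through.** **Inputs from the documents.** N = 46, attrition 10%, effect 1.1 servings/day, baseline mean 2.57 and SD 1.20, alpha 0.05 (Target Population and Accrual); two-sided tests (Statistical Analysis). 46 × 0.9 = 41.4, so 21+20 completers, with 20+20 as a check.

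**Assumptions, not in the documents.** 1:1 allocation; correlation r between baseline and month-3 intake; month-3 SD s, set to 1.20 unless stated otherwise.

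**1. Reproduce the plan's power.** SE = 1.20 × √(1/21 + 1/20) = 1.20 × 0.3124 = 0.375. The noncentral t distribution with 39 df gives 81.6% (80.6% at 20+20). 1.1/2.57 = 42.8%, which matches the stated 43%. The figure stands.

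**2. What it implies.** SD of change = √(1.20² + s² − 2r × 1.20 × s). With s = 1.20 this is 1.20 × √(2(1 − r)), which equals 1.20 at r = 0.50.

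**3. Planned test against adjusted test.** The adjusted SD is s√(1 − r²), with df = n − 3 and the variance multiplied by (n − 3)/(n − 4) = 38/37 for the estimated slope. At r = 0.50:
- Change: SD 1.20, SE 0.375, half-width 2.023 × 0.375 = 0.76.
- Adjusted: SD 1.20 × √0.75 = 1.039, SE 1.039 × 0.3124 × √(38/37) = 0.329, half-width 2.024 × 0.329 = 0.67.

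At 21+20, completers only:

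| s | r | Power, change | Power, adjusted | Half-width, change | Half-width, adjusted |
|---|---|---|---|---|---|
| 1.2 | 0.3 | 67.7% | 84.1% | 0.90 | 0.73 |
| 1.2 | 0.5 | 81.6% | 90.3% | 0.76 | 0.67 |
| 1.2 | 0.7 | 95.8% | 97.7% | 0.59 | 0.55 |
| 1.3 | 0.3 | 64.0% | 77.9% | 0.94 | 0.79 |
| 1.5 | 0.3 | 56.6% | 65.8% | 1.02 | 0.92 |
| 1.5 | 0.7 | 88.8% | 88.5% | 0.68 | 0.69 |

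Simulation of 20,000 trials per setting agrees: at s = 1.2, 0.818 against 0.903 (r = 0.5) and 0.676 against 0.839 (r = 0.3).

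**4. Dropouts.** A likelihood-based mixed model also uses the baselines of children lost before month 3. With 23+23 baselines and 21+20 completers, planned power is about 69% at r = 0.3 and 82.7% at r = 0.5. The completers-only table thus overstates the gain over the planned model by about 1 to 2 points.

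**5. Limits of gain and loss.** In large samples, the variance of change minus the adjusted variance is (1.20 − r × s)², which is never negative. It is zero when r × s = 1.20, for example s = 1.5 and r = 0.8, where power is 96.8% against 96.4%. In that no-gain case the largest loss over all effect sizes is 1.2 points.

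**6. SSB/SSS.** No SD is given for calories. Under equal SDs, only the large-sample variance ratio, adjusted to change, can be stated: (1 + r)/2, which is 0.65 at r = 0.3 and 0.75 at r = 0.5.

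**7. Removing the interaction.** With equal SDs and complete data, the remaining group term is the mean of the two visit differences: (0 + 1.1)/2 = 0.55. Simulation gave 0.55.

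**The case against.** The strongest reply is that the planned test is valid, its stated power reproduces, and the trial is exploratory. The mixed model already includes every participant, and the size of any gain rests on an r and a month-3 SD that the documents do not give. At r of 0.7 or more there is little to win. All of this stands. It limits the size of the point, but not its direction: adjustment costs almost nothing in the worst case and gains materially at the r implied by the plan's own SD.

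A reader might go further and infer that the trial is underpowered or that the power sentence is wrong. The documents do not support that. The 80% reproduces, and at r of 0.5 or more with equal SDs it holds for the planned test. A reader might also think the plan leaves open whether change or month-3 intake was powered. It does not: the powered outcome is named as 3-month change. What is missing is only the r or SD of change behind it.

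Two further cautions are fair. The half-widths are on the servings scale of the power section, whereas the Statistical Analysis section models cups/day; power survives a constant rescaling, but the half-widths do not. And the Objectives section words the hypothesis as percentage change from baseline, seen in one group but not the other. Neither the planned model nor the adjusted difference estimates that directly, so the primary estimand should be worded to match the chosen analysis.

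**Conclusion.** The point holds as an improvement in precision, not as an error. At r = 0.50 with equal SDs, adjustment takes power from about 82% to about 90% and the half-width from 0.76 to 0.67 servings/day. In precision this is worth about 53 completers instead of 41, since 41 × (0.758/0.666)² ≈ 53. At an assumed r = 0.3, power is about 68–69% against 84%. The gain is small at r of 0.7 or more and nil when r times the month-3 SD is about 1.20. Adjustment does not guarantee 80% if the month-3 SD is larger than assumed. All these figures rest on 1:1 allocation and the stated r and SDs.

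The removal rule is a distinct defect in the same analysis. After a non-significant interaction, the reported group term would be about half the true month-3 effect.

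**What to change.** 1. Make the primary FV and SSB/SSS comparison the month-3 group difference adjusted for baseline intake. A longitudinal model with baseline means constrained equal across groups is preferable, because dropouts' baselines still contribute; ANCOVA is the simpler alternative.
2. Report that difference with its 95% CI whatever its p-value.
3. Delete the rule that removes a non-significant group-by-time term.
4. Optional: state the r or SD of change behind the 80% power (SD 1.20 corresponds to r = 0.50 with equal SDs), and use one FV unit throughout.

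The document is written in the past tense. If the data have been analysed, report the adjusted result as a labelled post hoc analysis beside the planned model.

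The cost is a change of SAP wording, one degree of freedom and at most about 1 point of power. The baseline recalls are part of the existing design, so no new data or visits are needed.

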## **OBJECTIVES:**

Primary Aim: To test, in a 3-month randomized controlled trial, the efficacy of the mHealth intervention on changing consumption of targeted healthy and less healthy foods/beverages in children with ASD who are picky eaters. We hypothesized that, by the end of the intervention, children in the intervention group, but not children in the education group, would show a significant increase (expressed as % change from baseline) in intake of FV and a decrease in calories consumed from salty and sugary snacks and SSB.

Secondary Aim: To perform a comprehensive evaluation of the mHealth intervention by measuring parent and child engagement, motivation, user friendliness, and ease of use.

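### The group-by-time term is the intervention effect, yet the plan removes it when non-significant, leaving a final model with no estimate or confidence interval for that effect

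*Combined protocol and SAP*

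**What the plan says.** Section 5, Statistical Analysis, specifies a repeated-measures mixed model for fruit and vegetable (FV) intake and for calories from snacks and sweetened beverages (SSB/SSS). The fixed effects are group and time, and time has two levels, baseline and month 3. Baseline is therefore an outcome row and not a covariate. The section continues: "The group-by-time interaction was tested and removed if not significant".

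Three other places show which effect is wanted:

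- Target Population and Accrual takes "3-month changes in intake of targeted healthy foods (FV) as the primary outcome variable" and powers an increase "in the intervention group relative to the education group".
- The same section gives the project's primary purpose as feasibility, acceptability and utilization, and "to obtain preliminary effect size estimates".
- Objectives hypothesises that "children in the intervention group, but not children in the education group, would show a significant increase".

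Analysis of covariance is named only for subgroup questions. The analysis restricted to active participants is a sensitivity analysis with no estimator of its own. Nothing in the document constrains the baseline means to be equal, and nothing says that the interaction estimate or its interval is reported once the term has been removed.

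**The concern.** Dropping a non-significant interaction is a habit from factorial models, where the interaction is a side question and the main effects carry the message. Here the roles are reversed. The interaction is the treatment effect, and the main effects are by-products of having baseline in the outcome vector.

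Three things are at stake:

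- **The estimate.** Whether the final model contains the effect size depends on its P value. If the estimate from the testing step is not reported after removal, the published effects are selected for significance and are too large on average.
- **The group coefficient.** Once the interaction has gone, the group term may be read as efficacy. That is a second chance at significance, on a quantity that is not the effect.
- **The time coefficient.** It pools change over both arms. Under Study Procedures, "Parents in both groups were encouraged to promote children's intake of the healthy target foods", so a shared improvement is plausible and could be mistaken for an intervention effect.

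**Working it through.** **Inputs from the plan.** 46 children, 10% attrition, SD 1.20 servings/day (given for baseline), effect 1.1 servings/day, two-sided alpha 0.05, two-sample t-test.

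**Assumptions.** 21 and 20 completers (46 × 0.9 = 41.4; equal allocation is not stated); SD 1.20 at both visits; normal data; no change in the education arm unless stated. The correlation r between baseline and month 3 is not in the documents, so 0.3, 0.5, 0.7 and 0.8 are shown.

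**Step 1: the plan's own figure.** SE = 1.20 × √(1/21 + 1/20) = 1.20 × 0.3124 = 0.375. The noncentrality is 1.1/0.375 = 2.93 on 39 df, with critical value 2.023. Power is 81.6%, which agrees with the stated 80%. Also, 1.1/2.57 = 43%, as stated. The SD of change is 1.20 × √(2(1 − r)). Applying 1.20 to change, as the power calculation does, therefore corresponds to r = 0.5, the case closest to the plan.

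**Step 2: what each coefficient estimates.** Let the expected group difference be 0 at baseline (randomisation) and δ at month 3.

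- Interaction, full model: δ − 0 = δ.
- Group, reduced model: (0 + δ)/2 = δ/2. At δ = 1.1 this is 0.55.
- Time, reduced model: mean change over both arms, about δ/2 if the education arm does not change.

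This is algebra and does not depend on r. As a check, a mixed model was fitted to 100 simulated data sets (r = 0.5, δ = 1.1). The full-model interaction equalled the difference in mean change to rounding error. The average estimates were 1.09 (interaction), 0.52 (reduced-model group) and 0.55 (reduced-model time).

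**Step 3: how often the rule removes the term, and what survives.** Removal rates are from the noncentral t distribution; the rest is simulation, with at least 200,000 trials per scenario.

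| | r = 0.3 | r = 0.5 | r = 0.7 | r = 0.8 |
|---|---|---|---|---|
| 95% CI half-width, interaction | 0.90 | 0.76 | 0.59 | 0.48 |
| δ = 1.1: term removed | 32% | 18% | 4% | 0.5% |
| δ = 1.1: mean surviving estimate | 1.33 | 1.22 | 1.13 | 1.10 |
| δ = 1.1: CI would reach 1.1, among removed | 92% | 86% | 55% | 11% |
| δ = 0.55: term removed | 77% | 70% | 54% | 38% |
| δ = 0.55: mean surviving estimate | 1.12 | 0.97 | 0.80 | 0.69 |
| δ = 0.55: CI would reach 1.1, among removed | 71% | 58% | 23% | 2% |

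With no true effect, the term is removed in 95% of trials. The rows on whether the CI reaches 1.1 show what is lost. At r = 0.5, most of the intervals absent from the final model would still have been compatible with the design effect.

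**Step 4: if main effects are read as efficacy.** With equal variances at the two visits, a child's change and a child's mean are uncorrelated. Testing the interaction and then, after removal, the group effect gives a false-positive rate of about 0.05 + 0.95 × 0.05 = 9.75%; simulation gave 9.7% to 9.9%. If both arms instead improve equally by an assumed 0.3 servings/day, the pooled time effect is significant in 26% (r = 0.3) or about 34% (r = 0.5) of trials where the term is removed.

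**The case against.** The strongest reply is that the efficacy decision is sound. The interaction is tested at two-sided 5% before anything is removed, so alpha, power and sample size are untouched. It has to be estimated in order to be tested, so an estimate and interval exist, and the section does not say that they are withheld. It also does not say that the reduced-model group or time effect is read as efficacy; its reference to 3-month changes by group points to the interaction. All of this stands. The selection bias in Step 3 and the false positives in Step 4 are therefore conditional harms, and nothing in the document shows that either occurred.

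A second point is that the Objectives hypothesis is literally a within-arm pattern, significant change in one group but not the other. It is weaker support for a between-group contrast than the power statement is. That is fair, but it does not rescue the rule: a model without the interaction forces the same change on both arms and cannot represent that pattern either.

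Third, the wider figures in the table fit the plan less well. At r = 0.3 the power would be about 68% and at r = 0.8 about 99.5%, against a stated 80%. At r = 0.7 or above, the overstatement at the design effect is about 2% or less. The effects of 0.55 and 0.3 are illustrative, and the calculation uses completers only. This bears on size, and r = 0.5 should be read as the leading case.

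Finally, the trial is exploratory and has other purposes. Estimation is nevertheless one of the purposes it names, and an exploratory trial relies more on its intervals than on its P values.

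**Conclusion.** The rule is wrong as written. When the interaction is non-significant, the final model contains no estimate or interval for the intervention effect, and no other part of the plan supplies one. That conclusion follows from the model structure and rests on no assumed number. The significance test itself remains valid.

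On the reading closest to the plan's power calculation (r = 0.5), the rule bites in 18% of trials at the design effect and in 70% at half of it. If the removed estimates went unreported, the remainder would be overstated by 11% (1.22 against 1.1) and 77% (0.97 against 0.55). These sizes depend on the unstated correlation, on SD 1.20 at both visits and on 41 completers. The false-positive rate near 10% applies only if the reduced-model group effect is read as efficacy.

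**What to change.** Delete the removal clause from the sentence on the interaction in section 5. State that the group-by-time term stays in every FV and SSB/SSS model and that its estimate, 95% CI and P value are the primary result for that outcome, whatever the significance. Add that the group and time main effects are not interpreted as evidence of efficacy.

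The document is written in the past tense. If the analyses are complete, report the full-model interaction estimate and interval for each outcome and label this as a clarification of the plan. A month-3 comparison adjusted for baseline targets the same effect but is a different estimator, so it should not be substituted as the primary result after the data have been seen.

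The cost is one or two sentences of wording and, at most, refitting the full model for each outcome. No new data or participants are needed, and sample size and power stay as they are.
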